7.7 Safety Analysis

The Safety population will be used to summarize all adverse event data, unless otherwise specified. Safety data will be summarized separately, using the same approach, for both the blinded and unblinded enemas. Adverse events will be summarized for each randomization group through the 8-week primary endpoint follow-up. Adverse events occurring after the 8-week follow-up visit will be grouped into the following categories:

1. Group A, placebo randomized subjects who did not receive an unblinded RBX2660
2. Group B, RBX2660 randomized subjects who did not receive an unblinded RBX2660
3. Group C, placebo randomized subjects who went on to receive an unblinded RBX2660
4. Group D, RBX2660 randomized subjects who went on to receive an unblinded RBX2660

7.7.1 Adverse Events

Adverse events will be summarized using counts of the number of events and frequencies (counts and percentages) of the number of subjects by treatment group and overall. The incidence of each preferred term (PT) within the primary system organ class (SOC) as well as overall primary SOC incidence will be presented. Summaries may also be presented by PT, irrespective of SOC. A subject with multiple events coded to the same PT within a primary SOC will be counted only once for the PT within the primary SOC. Likewise, a subject with multiple events coded to the same SOC will be counted only once within the SOC.

An overall summary of AEs will present the incidence of (1) all TEAEs, (2) TEAEs related to IP, (3) TEAEs related to enema procedure, (4) TEAEs related to *C. difficile* disease, (5) TEAEs related to a preexisting condition, (6) serious TEAEs, (7) serious TEAEs related to IP, (8) serious TEAEs related to the enema procedure, (9) serious TEAEs related to *C. difficile* disease, (10) serious TEAEs related to a preexisting condition, and (11) TEAEs leading to death.

Frequency of occurrence and number and percent of subjects experiencing an event through 6 months follow-up will be presented by treatment for both the blinded and unblinded enemas as follows:

- All TEAEs
- TEAEs by maximum severity
- TEAEs by relatedness to IP
- TEAEs by relatedness to *C. difficile* disease
- TEAEs by relatedness to enema procedure
- TEAEs by relatedness to preexisting condition
- TEAEs resulting in subject withdrawal
- TEAEs resulting in death
- Serious TEAEs
- Serious TEAEs by maximum severity
- Serious TEAEs by relatedness to IP
- Serious TEAEs by relatedness to *C. difficile* disease
- Serious TEAEs by relatedness to enema procedure
- Serious TEAEs by relatedness to preexisting condition
- Serious TEAEs resulting in subject withdrawal
- Serious TEAEs resulting in death

For the summary of AEs by maximum severity, if a subject has multiple events occurring in the same SOC or same PT, then the event with the highest severity will be counted. For AEs reported by causality, if a subject has multiple events occurring in the same SOC or same PT, the event with the highest association will be summarized.

A summary of TEAE and serious TEAE characteristics (severity, relatedness to IP, relatedness to *C. difficile* disease, relatedness to enema procedure, and relatedness to preexisting condition by outcome) will also be presented by treatment and overall for both the blinded and unblinded enemas.

Incidence of AEs and serious AEs will also be presented by onset interval after the blinded and unblinded enemas for the following intervals:

- Baseline (onset date prior to date of blinded enema);

- IP administration (onset date on the date of the blinded or unblinded enema as applicable);
- and the following intervals relative to the last enema date (blinded or unblinded as applicable):
 - 1 Week (day 8), 4 Weeks (day 29), 8 Weeks (day 57), 3 Months (Day 90) and 6 Months (Day 180).

At the time of the primary efficacy analysis, all safety endpoints related to events occurring within 8 weeks following blinded treatment will be assessed. Additionally, other safety endpoints will be analyzed as the data allows during the primary efficacy analysis with a complete analysis to be provided with the full study results in the final analysis.

For data presentation, SOC will be ordered alphabetically, with PT sorted by decreasing total frequency. No inferential statistics will be provided for the AE data.

Subject listings will be presented for all AEs including SAEs.

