6.2 Time Point Algorithms

6.2.1 Relative Day

The date of study enema administration will be considered relative day 1, and the day before study enema administration will be relative day -1. Relative days will be calculated as follows only when the full assessment date is known (i.e., partial dates will have missing relative days, unless imputation methods have been specified):

For days before first enema:

Date of Assessment – Date of first enema administration

For days on or after first enema:

Date of Assessment – Date of first enema administration +1

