6.2.2 Windows

For the purpose of statistical analysis, the analysis visit windows will be calculated in terms of study days since the day of the study enema administration, as illustrated in the following tables:

Analysis Windows for Clinical Visits

Visit	Scheduled Study Day	Visit Window in Protocol (Days)	Visit Window for Analysis (Days)
Screening Visit	-30 through -1	-30 through -1	-30 through -10
Baseline/1 st Enema	1	1	1
Week 1 Office	8	5 - 11	5 - 11
Week 4 Office	29	26 - 32	26 - 32
Week 8 Office	57	54 - 60	54 - 60

Analysis Windows for Phone Assessments

Visit	Scheduled Study Day	Visit Window in Protocol (Days)	Visit Window for Analysis (Days)
Week 2 - Phone	15	12 - 18	12 - 18
Week 3 - Phone	22	19 - 25	19 - 25
Week 6 - Phone	43	40 - 46	40 - 46
3 month - Phone	90	76 - 104	76 - 104
6 month - Phone	180	166 - 194	166 - 194

If a subject has more than one assessment occurring in the same visit window, the data from the visit closest to the scheduled study day will be used for analysis. If two visits have the same distance from the scheduled study day, i.e., one visit occurs -1 day from study day, and the other visit occurs +1 day from study day, the data from the visit after the scheduled study day will be used for analysis.

Analysis Windows for Adverse Event Reporting by Onset Interval

Onset Interval Name	Onset Interval Analysis Window	Window for Analysis (Days)
Baseline	Screening - < Baseline	≤ -1
1-week	Baseline - 1-week	1 through 8
4-week	> 1-week - 4-week	9 through 29
8-week	> 4-week - 8-week	30 through 57
4-month	> 8-week - 4-month	58 through 121
6-month	> 4-month - 6-month	122 through 180+

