6.5.3.4 Treatment-Emergent Adverse Events

Adverse events will be considered treatment-emergent adverse events (TEAE) according to the following algorithm:

- If the complete onset date of an AE is known, then:
 - If AE onset date is prior to initial treatment date, then the AE will not be considered treatment-emergent.

- If AE onset date occurs on or after initial treatment date, then the AE will be considered treatment-emergent.
- If AE onset date is partially known, then:
 - If day is unknown, and month/year occurs on or after first enema month/year, then AE will be considered treatment-emergent. Otherwise, AE will not be considered treatment-emergent.
 - If month/day is unknown, and year occurs on or after first enema year, then AE will be considered treatment-emergent. Otherwise, AE will not be considered treatment-emergent.

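### The 6-month adverse event tables use crude counts and percents, although blinded follow-up is expected to be shorter on placebo than on RBX2660

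*SAP*

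**What the plan says.** SAP 7.7.1 sets the format of the main adverse event tables. Besides event counts, the "number and percent of subjects experiencing an event through 6 months follow-up will be presented by treatment for both the blinded and unblinded enemas". SAP 7.7 adds that "Safety data will be summarized separately, using the same approach, for both the blinded and unblinded enemas", and that "Adverse events will be summarized for each randomization group through the 8-week primary endpoint follow-up". Events after the 8-week visit go into four groups, defined by randomised arm and by whether an unblinded RBX2660 enema was received.

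On timing, SAP 6.5.3.4 gives a start only: "If AE onset date occurs on or after initial treatment date, then the AE will be considered treatment-emergent". SAP 6.2.1 counts days from the first enema. The onset-interval tables in SAP 7.7.1 count from the last enema. The interval sets also differ: the table headed "Analysis Windows for Adverse Event Reporting by Onset Interval" in SAP 6.2.2 uses days 58 to 121 and then 122 onwards, while SAP 7.7.1 uses day 90 and day 180.

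Protocol 3.8 and 6.14 allow a documented failure to take an unblinded RBX2660 enema within 21 days, after which follow-up restarts. SAP 4.1 exits a subject with an on-study episode whose treatment plan lies outside the protocol. Protocol 3.8 keeps failures without an unblinded enema on their original schedule, and withholds the product when failure is not conclusively documented.

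**The concern.** A crude percent through 6 months compares arms fairly only if both are observed for about the same time. Here the reason for leaving blinded follow-up is the efficacy outcome itself, so a working product keeps its own subjects under blinded observation longer. RBX2660 can then show more adverse events than placebo with no true difference in hazard. The distortion matters most for events that accrue steadily, since events clustered just after the enema are mostly captured before anyone leaves.

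The SAP plans Kaplan-Meier estimates for CDI recurrence but nothing similar for adverse events, so a reader of the 6-month tables would have no planned estimate that allows for the difference in follow-up.

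**Working it through.** **Inputs from the documents.** Success 69% and 47% (SAP 4.4), hence failure 31% and 53%; about 180 RBX2660 and 90 placebo subjects; unblinded enema within 21 days of failure; 66.5% of events from baseline through the 7-day visit in the first Phase 2 study (Protocol 1.5.1).

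**Plan's own figures.** A two-proportion calculation for 47% vs 69%, 2:1, two-sided 5%, 90% power gives 78 placebo subjects and 234 in total. At 80 and 160 (the plan's 240) power is 91.0%, in line with the stated figure. Exponential hazards from the same rates, 104 per arm over 6 months, give log-rank power of 99.55% against the SAP's 99.5%.

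**Assumptions.** Failure uniform over weeks 1 to 8; leaving 1 to 3 weeks later; half to all failures leave; same true hazard in both arms; blinded events end at the unblinded enema or exit. This trial's uptake is unknown. In Phase 2b (Protocol 1.5.2) there were 44 − 20 = 24 placebo failures, and 24 placebo subjects were assessed after open-label RBX2660.

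**Leavers (upper bound).** Placebo 0.53 × 90 = 47.7; RBX2660 0.31 × 180 = 55.8. The proportion, not the head count, is higher on placebo.

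**Mean blinded follow-up.** Leavers average 4.5 + 2 = 6.5 weeks; others 26.
- All leave: placebo 0.47 × 26 + 0.53 × 6.5 = 15.7; RBX2660 0.69 × 26 + 0.31 × 6.5 = 20.0.
- Half leave: placebo 0.735 × 26 + 0.265 × 6.5 = 20.8; RBX2660 0.845 × 26 + 0.155 × 6.5 = 23.0.

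**Events per subject, RBX2660/placebo.**
- Constant hazard: the ratio of follow-up times, 1.274 (all) or 1.103 (half).
- Front-loaded (66.5% in week 1, the rest even over 25 weeks): a leaver accrues 0.665 + 0.335 × 5.5/25 = 0.739 of the 6-month total. All leave: (0.69 + 0.31 × 0.739)/(0.47 + 0.53 × 0.739) = 0.919/0.862 = 1.067. Half leave: 0.960/0.931 = 1.031.

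**Percent of subjects at a true 50% risk.** Front-loaded, a leaver's risk is 1 − 0.5^0.739 = 0.401.

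| Case | RBX2660 | Placebo | Gap (points) |
|---|---|---|---|
| Front-loaded, all leave | 46.9% | 44.7% | 2.2 |
| Front-loaded, half leave | 48.5% | 47.4% | 1.1 |
| Constant, all leave | 39.4% | 31.9% | 7.5 |
| Constant, half leave | 44.7% | 40.9% | 3.8 |

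The standard error of the difference is about √(0.25/180 + 0.25/90) = 6.4 points.

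A second constant-hazard model, with exponential failure times and 7 to 21 days to the unblinded enema, gave ratios of 1.10 to 1.31 at a true 30% risk.

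**Serious events.** Protocol 7.1 makes a recurrence hospitalised for at least 24 hours a serious event. Take a 20% true risk of other serious events, plus an assumed 0, 10 or 20% risk of a CDI serious event per failure. RBX2660 minus placebo, in points:

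| Case | 0% | 10% | 20% |
|---|---|---|---|
| Constant, all leave | +3.2 | +1.1 | −1.0 |
| Front-loaded, all leave | +1.1 | −0.8 | −2.7 |
| Constant, half leave | +1.6 | −0.3 | −2.2 |
| Front-loaded, half leave | +0.5 | −1.3 | −3.1 |

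**Before week 8.** Under this timing 5/7 of leavers cross before week 8. If all failures take the unblinded enema, that is 0.53 × 5/7 = 38% of placebo and 0.31 × 5/7 = 22% of RBX2660 subjects. If their events are cut off there, the week-8 gap stays under one point (40.6% vs 40.4% front-loaded; 17.9% vs 17.0% constant).

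**The remedy.** With risk independent of failure, censored Kaplan-Meier returns 50% in both arms, but that follows from the assumption. Suppose failures carry twice the hazard (constant, all leave). The true gap is (0.69 × 0.50 + 0.31 × 0.75) − (0.47 × 0.50 + 0.53 × 0.75) = 0.5775 − 0.6325 = −5.5 points. Kaplan-Meier gives about −2 by simulation. The crude percents give about (0.345 + 0.31 × 0.293) − (0.235 + 0.53 × 0.293) = +4.6, where 0.293 = 1 − 2^(−0.5) is a leaver's risk at 6.5 weeks.

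**The case against.** The strongest reply is that the SAP already limits the problem. The randomised comparison it specifies is to week 8, which is almost untouched if events are cut off at the unblinded enema. After week 8, Groups A and B contain only subjects with no unblinded enema, so that enema does not truncate their follow-up. On the only timing evidence in the documents, the distortion for all events is 1.1 to 2.2 points against a standard error of 6.4. SAP 7.7.1 also says "No inferential statistics will be provided for the AE data". Enema timing, discontinuation reasons and full listings will be reported. All of this stands and keeps the point optional. However, Groups A and B are defined by what happened after randomisation, so A against B is not a randomised comparison. The 6-month tables in SAP 7.7.1 still carry no allowance for follow-up time.

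A reader might go further and infer that, with no written cut-off, the 6-month placebo column would absorb events after RBX2660 exposure (20 to 40% of its follow-up under the assumptions above), so that the comparison could change direction. The documents do not support this over 6 months. SAP 7.7 requires separate summaries for blinded and unblinded enemas, and after week 8 places placebo subjects who took unblinded RBX2660 in a group of their own. The assignment question stays open only for events after an early unblinded enema in the by-arm week-8 table.

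**Conclusion.** The point holds as an optional reporting improvement, with medium confidence. Reading SAP 7.7.1 together with SAP 7.7, blinded follow-up is expected to be shorter on placebo, and the crude 6-month tables then lean against RBX2660 when the true hazards are equal. The excess is 3 to 7% in events per subject if events are front-loaded and 10 to 27% if they accrue steadily. It is small for all events taken together and matters more for late or steadily accruing events. For serious events no direction can be claimed, because the CDI component is a true difference that runs the other way.

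These sizes rest on the design success rates, on half to all failures leaving, and on assumed failure timing. The 53% and 31% are upper bounds. The missing assignment rule and the two interval sets are gaps in detail. No test, alpha or stopping rule is affected.

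**What to change.** In SAP 7.7.1:
1. Assign each adverse event to the most recent enema before its onset, and apply the same rule to the by-arm week-8 table.
2. For all TEAEs, related TEAEs and serious TEAEs, add by randomised arm a Kaplan-Meier or cumulative-incidence estimate of time to first event from the blinded enema, censored at the unblinded enema, exit or 6 months.
3. Give person-time rates within one common set of onset intervals, replacing the two sets now in SAP 6.2.2 and 7.7.1.
4. Keep the crude tables.

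Do not collapse step 3 into a single pooled rate. With front-loaded events and no true difference it would favour RBX2660 by 7 to 16%: all leave, (0.919/19.96)/(0.862/15.67) = 0.84; half leave, (0.960/22.98)/(0.931/20.83) = 0.93.

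The cost is some SAP wording and a few extra tables, built from enema, exit and onset dates already collected. The censored estimates assume that leaving is unrelated to adverse event risk. That is doubtful for CDI-related serious events, so they reduce the bias without removing it.

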7.7.2 Other Analyses Related to Safety

7.7.2.1 Subject Diary including Solicited Adverse Events and Compliance

All solicited adverse events recorded in the Subject Diary will be summarized utilizing frequencies (number of events), proportions (number of subjects with the event) and 95% CIs for categorical variables and using the descriptive statistics as listed in Section 8.1 for continuous variables.

For each solicited event, severity scores will be summarized as both categorical and continuous values. For continuous summaries, severity scores will be identified as either pre-treatment or post-treatment (all diary entries captured after the blinded and unblinded enemas), and the average for each period will be calculated across individual subjects. Baseline for continuous summaries will be considered the average during the pre-treatment period. For categorical summaries, if a subject reports more than one severity score on the same date, the maximum

severity will be used. Baseline for categorical summaries will be considered the last non-missing assessment prior to the blinded enema.

For each categorical summary of event frequency, a two-sided 95% CI will be calculated using the normal approximation of the binomial.

The following summaries will be produced separately for the blinded enemas and unblinded enemas:

- Frequency of severity scores on day of enema administration by treatment and overall
- Frequency of severity scores on day 1 through 1-week post-treatment by treatment and overall
- Frequency of maximum post-treatment severity score by treatment and overall

The following summaries will be produced for the double-blind phase only:

- Summary of average severity score and change from baseline by treatment and overall
- Shift from baseline to 1-week post-treatment severity score by treatment and overall
- Shift from baseline to maximum post-treatment severity score by treatment and overall

The following summary will be produced during the final analysis as related to the overall scores:

- Summary of average severity scores by treatment and overall

Compliance in returning the Subject Diary will be calculated by dividing the number of diaries turned in, whether complete or not, by the number of diaries expected to be turned in.

Furthermore, compliance will be summarized by calculating the proportion of subjects who turned in “complete” diaries, where complete is defined as answering all 11 daily questions for at least 80% of the expected number of diaries. Compliance will be calculated following both the blinded and unblinded enemas separately and summarized by treatment group.

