4.4 Determination of Sample Size

To demonstrate a 69% success with one dose of the RBX2660 treatment group vs. 47% success in the Placebo control group, 240 subjects are required (power > 90%, nominal 2.5% type I error rate). Up to an additional 30 subjects will be enrolled to allow for a 10% loss-to-follow up rate, for a total of approximately 270 subjects. Considering the 2:1 randomization, this results in approximately 180 subjects in the RBX2660 arm and 90 subjects in the Placebo arm. Enrolled subjects who have signed consent and withdraw for any reason prior to administration of the first blinded enema will be replaced without counting toward the sample size cap. Replacement subjects will be randomized to ensure proper blinding.

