8 STATISTICAL METHODS

8.1 General Methodology

All statistical tests will be two-sided with a significance level of $\alpha=0.05$, unless specified otherwise, and will be performed using SAS® Version 9.3 or higher. Confidence intervals (CI) will be constructed at the level of 95% unless specified otherwise. For continuous variables,

descriptive statistics (number of subjects [N], mean, standard deviation [SD], median, interquartile range [IQR], minimum, and maximum) will be generated. For discrete/categorical variables, the number and percentage of non-missing subjects will be generated. Descriptive statistics will be provided by treatment arm for all subjects. Standard operating procedures (SOPs) will be followed in the creation, validation and quality control of all data displays and analyses.

Subject listings of all data from the eCRFs as well as any derived variables will be presented.

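### The normal-approximation 95% CIs for solicited diary events fail in sparse cells: 0% to 0% at zero events, and coverage well below 95% at true rates of about 2% or less

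*SAP*

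**What the plan says.** SAP 7.7.2.1 covers the solicited events recorded in the Subject Diary. Its opening sentence attaches 95% CIs to the categorical summaries, and the method follows for each of them: "a two-sided 95% CI will be calculated using the normal approximation of the binomial". SAP 8.1 adds only the level: "Confidence intervals (CI) will be constructed at the level of 95% unless specified otherwise". Neither section gives an exact or score interval, or a rule for zero counts.

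Eleven solicited symptoms are listed in SAP 6.5.4.1. They run from gas and bloating to rectal bleeding, vomiting and fever. SAP 7.7.2.1 treats severity as categorical as well as continuous. Its list of tables includes "Frequency of severity scores on day of enema administration by treatment and overall" and "Frequency of maximum post-treatment severity score by treatment and overall", produced separately for blinded and unblinded enemas.

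Other safety data are handled differently. Under SAP 7.7.1, treatment-emergent and serious adverse events and deaths are given as counts and percentages, without inferential statistics. SAP 7.7.2.2 summarizes major CDI complications as incidence and specifies no CI.

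**The concern.** The normal-approximation (Wald) interval takes its width from the observed proportion. When few or no subjects have an event, the estimated standard error is too small, or zero, and the interval is too short. Splitting eleven symptoms by severity grade, arm and enema type makes low counts plausible, particularly after unblinded enemas, which go only to treatment failures who elect one.

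At stake is the face value of the printed table. A row showing 0% with a 95% CI of 0% to 0% for, say, severe rectal bleeding tells the reader that the rate is known to be zero, when 0/90 is compatible with a rate of up to about 4%.

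**Working it through.** **Inputs**
- Method and level: Wald, two-sided 95% (SAP 7.7.2.1, 8.1).
- Denominators: SAP 4.4 says "this results in approximately 180 subjects in the RBX2660 arm and 90 subjects in the Placebo arm", so n = 90, 180 and 270 overall.
- Unblinded enemas: no number is given. Assumption: about 50 per randomized arm. At the planning success rates, failures are 0.31 × 180 ≈ 56 and 0.53 × 90 ≈ 48, if all elect the enema.
- True rate of a severe solicited symptom: not given. Assumed range 0.2% to 10%.

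**The plan's own figures.** For 47% against 69% at 2:1, two-sided 0.05 and 90% power, the usual two-proportion formula gives 78 + 156 = 234. At 80 + 160 = 240 the power is 91.0%, consistent with SAP 4.4. Adding 30 gives 270, which splits 180:90. The denominators are therefore sound. The only figure attached to the CIs themselves is the nominal 95%.

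**Zero events.** Wald: p̂ ± 1.96·√(p̂(1−p̂)/n) with p̂ = 0 is [0, 0] for every n. The exact (Clopper-Pearson) upper limit is 1 − 0.025^(1/n): 4.0% at 90, 2.0% at 180, 1.4% at 270. The Wilson upper limits are 4.1%, 2.1% and 1.4%.

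**One event**
- n=90: p̂ = 1.11%, half-width 1.96·√(0.0111 × 0.9889/90) = 2.17%, so Wald is −1.1% to 3.3%. Clopper-Pearson is 0.03% to 6.0%.
- n=180: p̂ = 0.56%, half-width 1.09%, so Wald is −0.5% to 1.6%. Clopper-Pearson is 0.01% to 3.1%.

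The Wald lower limit is negative for one to three events at n = 90, 180 and 270. Truncating it at zero would change neither the upper limit nor the coverage.

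**Coverage.** For each n and true rate p, sum the binomial probabilities of every count whose Wald interval contains p:

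| Assumed true rate | n=90 | n=180 | n=270 |
|---|---|---|---|
| 0.2% | 16.5% | 30.3% | 41.7% |
| 0.5% | 36.3% | 59.4% | 74.1% |
| 1% | 59.5% | 83.4% | 93.2% |
| 2% | 83.5% | 87.3% | 90.4% |
| 3% | 93.0% | 90.0% | 90.1% |
| 5% | 93.8% | 94.0% | 91.7% |
| 10% | 94.6% | 94.1% | 95.0% |

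From 20% to 50%, coverage is 94.1% to 95.6%.

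At the lowest rates the shortfall comes almost entirely from the zero-width interval. At p = 1% and n = 90, the chance of zero events is 0.99^90 = 40.5%, and 100% − 40.5% = 59.5%, the tabulated coverage. At n = 180 the chance of zero events is 16.4%.

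At the assumed unblinded n = 50, coverage is 39.5% at 1%, 63.5% at 2%, 92.0% at 5% and 87.9% at 10%.

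**Alternatives.** Over 0.2% to 10% at n = 90, 180 and 270, Clopper-Pearson covers 95.4% to 99.4% and Wilson 89.8% to 98.6%.

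**The case against.** The strongest reply is that little depends on these intervals. They apply to eleven diary symptoms in descriptive tables. The safety stopping rules (Protocol 7.12, SAP 8.5.1) rest on DSMB judgement. Counts are reported, so a reader can work out an exact limit. This stands as a limit on importance. It does not make a 0% to 0% interval correct.

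A second reply is that the poor coverage figures rest on rates the documents do not supply. That is right, and it is why a range is shown. What the protocol reports points to solicited events being common overall: in the first Phase 2 study (Protocol 1.5.1), 51.5% (17/33) of single-treatment subjects reported one on Day 7. In the earlier Phase 2B study (Protocol 1.5.2), 90.8% of adverse events were mild to moderate. That is a share of events, so it gives no per-symptom rate. The zero-event and one-event results need no rate assumption.

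A third reply is that the CI sentence may cover only the proportion of subjects with each symptom, and not the severity tables listed after it. The wording (each categorical summary), together with the treatment of severity as categorical, favours the wider reading but does not settle it. Under the narrower reading fewer cells are sparse.

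Two stronger readings are tempting, and the documents support neither:
- A reader might infer that the intervals misstate the events that matter most for safety. Serious events, deaths and major complications have no CI specified, so the defect does not reach them.
- A reader might extend the point to the pseudo-site proportions in SAP 8.6. That section asks for 95% CIs but names no method, so nothing there is shown to be wrong. Its outcomes are treatment success rates, planned at 47% and 69%, not rare events.

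**Conclusion.** The concern holds for sparse solicited-event cells only. At zero events the planned interval has no width at any sample size. At one event its upper limit is about half the exact one. Per-arm coverage is far below 95% at true rates of about 1% or less, and clearly below at 2% (84% at n=90, 87% at n=180). By 5% it is about 94% in each blinded arm, so common symptoms are adequately served there. In the smaller unblinded groups the shortfall extends to higher rates, subject to the assumed n of 50.

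The coverage figures depend on assumed rates. How many cells are affected depends on those rates and on whether the CI sentence covers severity grades. The consequence is a misleading descriptive table. Efficacy testing, the success criteria and safety stopping are unaffected. This is a minor point, but worth correcting.

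**What to change.** In SAP 7.7.2.1, replace the normal approximation of the binomial with the Clopper-Pearson exact interval for single proportions. The Wilson score interval is an acceptable alternative if shorter intervals are preferred, with the caveat that its coverage can dip below 95% at very low rates. In the same sentence, state whether the CIs apply to the severity-grade tables or only to the proportion of subjects with each symptom.

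The cost is one option in the SAS procedure. Intervals for rare events become wider and, with Clopper-Pearson, somewhat conservative. Sample size, power and data collection do not change.
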